3.2 Primary Efficacy Outcome

The primary efficacy outcome will be the proportion of PTS positive subjects defined as the ratio of PTS-positive subjects to total number of subjects in each study arm/group. PTS positive will be defined as all subjects who in audiogram are identified as having a permanent threshold shift (PTS) of ≥ 10 dB HL increase at any frequency from 2-6 kHz after shooting as compared to baseline audiogram. A SAS code will be written to code as PTS positive all the officers for whom the difference at any frequency from 2-6 kHz in hearing thresholds (30 days (+/- 3 days) post shooting - Baseline) will be ≥ 10 dB HL in at least one of the ears. If this difference is less than 10 dB then the officers will be coded as non-PTS positive.

To date, there are no reports of ZNS being associated with hearing damage or loss, so the hypothesis for this study will be a one-sided hypothesis.

For the primary outcome measure, the null and alternative hypotheses are provided below.

Comparison of the proportion of PTS-positive subjects between ZNS group and Placebo

$$H_0: p_{ZNS} - p_{Placebo} = 0 \quad H_A: p_{ZNS} < p_{Placebo}$$

We hypothesize that ZNS will reduce the proportion of PTS-positive officers by an absolute difference of 25% as compared to placebo. Our one-sided hypothesis is supported by animal studies, and lack of any evidence of hearing loss as a side effect of ZNS in human studies.

Hypothesis testing for the primary outcome will be performed at the one-sided alpha level of 0.025.

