7.1.1 Analysis of primary outcome variable

Efficacy analysis at the end of the study

The primary outcome measure for assessing effectiveness of ZNS (100 mg PO) post-shooting compared to the placebo group will be the proportion of officers with TTS defined as PTS positive 30 days (+/- 3 days) after shooting range exposure.

Audiogram will be performed to look for PTS. Officers for whom the difference at any frequency from 2-6 kHz in hearing thresholds (30 days (+/- 3 days) post-shooting - Baseline) is ≥ 10 dB HL will be defined as PTS positive. Primary analysis and sensitivity analyses will be carried out on the primary endpoint.

Primary analysis

Frequency and relative frequency will be used to describe the distribution of the primary outcome measure in each study group. To assess efficacy, Fisher's exact test will be used to compare the proportion of officers with PTS positive in ZNS group with the proportion of officers with PTS positive in the placebo group.

The confidence intervals will be calculated using method 10 described by Newcombe RG, 1998 and also described by Altman et al.

1. Altman, Douglas, et al., eds. Statistics with confidence: confidence intervals and statistical guidelines. <https://www.amazon.com/Statistics-Confidence-Intervals-Statistical-Guidelines/dp/0727913751>

Let n_1 be the number of participants in placebo group, and r_1 the number of participants with PTS in the placebo group. $p_1=r_1/n_1$ be the proportion of PTS in the placebo group, and q_1 the proportion of participants that do not have PTS in placebo group.

l_1 and u_1 are the lower and upper limits of the $100(1-\alpha)\%$ confidence interval for p_1

Using Wilson method we calculate:

$$A_1 = 2r_1 + z^2$$

$$B_1 = z\sqrt{z^2 + 4r_1 q_1}$$

$$C_1 = 2(n_1 + z^2)$$

$$l_1 = \frac{(A_1 - B_1)}{C_1} \quad u_1 = \frac{(A_1 + B_1)}{C_1}$$

z_α = the $100(1 - \alpha)^{th}$ percentile of the standard Normal distribution.

Let n_2 be the number of participants in ZNS group, and r_2 the number of participants with PTS in the ZNS group. $p_2 = r_2/n_2$ be the proportion of PTS in the ZNS group, and q_2 the proportion of participants that do not have PTS in ZNS group.

l_2 and u_2 are the lower and upper limits of the $100(1-\alpha)\%$ confidence interval for p_2

$$A_2 = 2r_2 + z^2$$

$$B_2 = z\sqrt{z^2 + 4r_2q_2}$$

$$C_2 = 2(n_2 + z^2)$$

$$l_2 = \frac{(A_2 - B_2)}{C_2} \quad u_2 = \frac{(A_2 + B_2)}{C_2}$$

The proportion difference between groups is: $D = p_1 - p_2$

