The lower (l_D) and the upper limits (u_D) of $100(1-\alpha)\%$ confidence interval for D will be calculated as:

$$l_D = D - \sqrt{(p_1 - l_1)^2 + (u_2 - p_2)^2}$$

$$u_D = D + \sqrt{(p_2 - l_2)^2 + (u_1 - p_1)^2}$$

To provide an estimate of treatment effect a supportive logistic regression analysis will be done with covariates: age, pre-existing hearing loss dichotomized to normal to minimal hearing loss and slight to mild loss, noise exposure history dichotomized to high risk and low risk, average post-shooting.

Sensitivity analysis of the primary endpoint

The potential impact of missing primary endpoint data will be explored in sensitivity analyses using multiple imputation. Two sensitivity analyses performed:

Sensitivity 1: MI analysis under the missing not at random assumption (MNAR)

Sensitivity 2: Logistic regression tipping point analysis under the assumption of data missing at random.

Sensitivity 1.

Proc MI procedure in SAS will be used to impute missing data for study treatment groups using the distribution implied by the non-missing officer data within the placebo group. The SAS code to impute data for Sensitivity analysis 1 under the MNAR assumption will be of the form:

```
PROC MI DATA=X SEED=<value> NIMPUTE=10 OUT=MI_OUT1 NOPRINT;
CLASS GROUP;
VAR AGE PTA LSurg....;
FCS LOGISTIC(PTS);
RUN;
```

Post imputation each of the imputed 10 datasets will be analyzed using the same approach as for the primary outcome measure. The estimates of the analysis of the 10 imputed datasets will be then combined following Rubin's rules using PROC MIANALYZE procedure in SAS which will be of the form:

```
PROC MIANALYZE PARMs=GMPARMS COVB=GMCOVB PARMINFO=GMPINFO WCOV BCOV
TCOV; / *dataset "gmparms" contains the estimates and associated standard errors
for the mean parameters from each of the M=10 imputed data sets.
dataset "gmcovb" contains the asymptotic covariance matrices
dataset "gmpinfo" contains parameter info*/
MODELEFFECTS INTERCEPT AGE PTA LSurg....;
RUN;
```

Sensitivity 2.

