Multiple imputation will be used to impute data in each of the study groups. A progressive penalty of $\delta_i = k_i \times \log(OR)$ will be added to imputed values in ZNS arm where (i) OR is the Odds ratio estimate for ZNS as compared to Placebo from the primary logistic regression analysis and (ii) $k_i = 1, 0.95, 0.90, \dots, 0.05, 0, 1.05, 1.10, \dots$ thus k ranges from 1 (equivalent to MI approach based on MAR) to 0 (or higher), until the conclusion of the primary analysis is overturned (i.e., $p < 0.05$ is lost at, this value of k_i being the 'tipping point'). Rubin's method will be used to combine the primary endpoint treatment effects across imputations for each value, k_i , of the penalty. Forest plots will be used to graphically display the penalty value that results in loss of statistical significance.

SAS code sample for Sensitivity analysis is provided below:

```
**Step 1: Generate 10 datasets by imputing the missing data**;

PROC MI DATA=X SEED=<value> NIMPUTE=10 OUT=MI_OUT1 NOPRINT;
CLASS GROUP;
VAR AGE PTA LSurg....;
FCS LOGISTIC(PTS);
RUN;

**Step 2: Generate 10 complete datasets from the 10 monotonized datasets in Step 1 for
missing values in the drug arm,
subtract DELTA derived above from their imputed data.**;
proc mi data=YYY NIMPUTE=1 SEED=<value> OUT=YYY_shift;
by group;
class group;
var AGE PTA LSurg....;
monotone method=logistic;
mnar adjust(PTS / shift=DELTA adjustobs=(group='1'));
run;

**Step 3: Apply the primary MMRM to the 10 complete datasets in Step 2**;
proc genmod data=YYY_shift descending;
```

```
by _imputation_;
class group;
model PTS = group AGE PTA LSurg.....;
ods output GEEModPEst=gmparms;
run;

**Step 4: Obtain the pooled inference from 10 sets of estimates from Step 3**;

PROC MIANALYze PARMS=GMPARMS COVB=GMCOVb PARMINFO=GMPINFO WCOV BCOV
TCOV;
MODELEFFECTS group;
RUN;
```

7.1.2 Analysis for secondary outcome measures.

The focus of the study is to determine efficacy of ZNS for treatment of acute hearing loss based on the testing of the hypothesis for the primary outcome. In addition, we will also conduct analysis to evaluate other important audiologic measures. The secondary outcome measures are key audiological and clinical assessments of hearing loss, and include: Audiometric TTS, DPOAEs, Ultra-high frequency audiometry, ECochG, and WIN testing 30 days (+/- 3 days) after shooting, and are measured as continuous level variables. We do not plan any adjustment of alpha error for multiple comparisons.

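### SAP 7.1.1 labels its confidence intervals 100(1−α)% but builds them with z at the 100(1−α)th percentile, and states no numeric level

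*SAP*

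**What the plan says.** The primary estimand in SAP 3.1 is the difference between arms in the proportion of PTS-positive officers. For its interval, SAP 7.1.1 states: "The confidence intervals will be calculated using method 10 described by Newcombe RG, 1998". It sets out Wilson limits arm by arm, (A − B)/C and (A + B)/C, with a single z in A, B and C. For placebo, "l_1 and u_1 are the lower and upper limits of the $100(1-\alpha)\%$ confidence interval for p_1", and the ZNS arm is worded the same way. For the difference, "The lower (l_D) and the upper limits (u_D) of $100(1-\alpha)\%$ confidence interval for D will be calculated as", followed by the method 10 square-root expressions. The definition of the critical value is "z_α = the $100(1 - \alpha)^{th}$ percentile of the standard Normal distribution". The formulas themselves use a bare z without the subscript.

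No numeric α or confidence level is attached to these intervals. SAP 3.2 fixes the test level: "Hypothesis testing for the primary outcome will be performed at the one-sided alpha level of 0.025". The tipping-point analysis in SAP 7.1.1 uses a different figure, continuing "until the conclusion of the primary analysis is overturned (i.e., $p < 0.05$ is lost at" the tipping value, and does not say whether that p is one- or two-sided. Neither figure is tied to the interval. The only numeric confidence level in the SAP is the 95% used to judge DPOAE change in SAP 3.3. Protocol 12.2.1 has no interval formula.

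**The concern.** A two-sided interval at level 100(1−α)% needs the 100(1−α/2)th Normal percentile. The SAP's percentile leaves α in each tail, not α/2. Since α also has no stated value, two programmers could follow the text faithfully and deliver different limits under different labels.

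This is the only interval the SAP specifies for the risk difference; the logistic model is described as supportive and yields an odds ratio. What is at stake is how precisely the main result appears to be estimated, and whether a trial that misses on Fisher's test is reported beside an interval that seems to exclude zero. The interval has no stated decision role, so the trial's formal conclusion is not at stake.

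**Working it through.** **Inputs.** 66 per arm, 50% placebo and 25% ZNS, one-sided 0.025 (SAP 2.7 and 3.2); Fisher's exact test, Wilson and method 10 formulas (SAP 7.1.1).

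**The plan's own figure.** The SAP gives no width or level for the intervals, so the only figure to reproduce is the 80.5% power. The arcsine approximation with continuity correction gives Φ(√132 × |asin√(0.5 − 1/132) − asin√(0.25 + 1/132)| − 1.96) = 80.5%. Full enumeration of one-sided Fisher gives 81.3%. The design inputs are therefore read correctly.

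**Level implied by the written z.** Limits at ±z(1−α) have nominal level 2Φ(z(1−α)) − 1 = 1 − 2α. Coverage below comes from enumerating all 67 × 67 outcomes at 66 per arm, 50% versus 25%.

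| α entered | Label | z as written | Nominal level | Exact coverage |
|---|---|---|---|---|
| 0.01 | 99% | 2.326 | 98% | 97.9% |
| 0.025 | 97.5% | 1.960 | 95% | 94.9% |
| 0.05 | 95% | 1.645 | 90% | 90.2% |
| 0.10 | 90% | 1.282 | 80% | 80.4% |

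**Width and agreement with Fisher.** Disagreement here means that the lower limit for D (placebo minus ZNS) is above zero while one-sided Fisher p exceeds 0.025.

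| z | Mean width, 50% vs 25% | Disagreement, 50% vs 25% | Disagreement, 50% vs 50% |
|---|---|---|---|
| 1.645 | 0.262 | 9.9% | 3.4% |
| 1.960 | 0.310 | 4.3% | 0.8% |
| 2.241 | 0.352 | 0% | 0% |

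The narrowing from 1.960 to 1.645 is 1 − 0.2617/0.3099 = 15.6%.

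**Worked case: 33/66 placebo, 22/66 ZNS.** D = 0.5000 − 0.3333 = 0.1667, one-sided Fisher p = 0.039.

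- z = 1.645: Wilson limits are 0.4008 to 0.5992 (placebo) and 0.2461 to 0.4337 (ZNS).
  - Lower limit: 0.1667 − √[(0.5 − 0.4008)² + (0.4337 − 0.3333)²] = 0.026.
  - Upper limit: 0.1667 + √[(0.3333 − 0.2461)² + (0.5992 − 0.5)²] = 0.299.
- z = 1.960: Wilson limits are 0.3827 to 0.6173 and 0.2316 to 0.4534. The same expressions give −0.001 to 0.322.

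The choice of α alone decides whether the interval excludes zero in a trial that is not significant at 0.025.

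**Correcting the percentile only.** With the 100(1−α/2)th percentile but α entered as 0.025, z = 2.241. Coverage is 97.4%, and the interval includes zero while Fisher is significant in 3.3% of trials at 50% versus 25%. With z = 1.645 or 1.960 that never happens at this sample size.

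**The case against.** The strongest reply is that the level is not really open. The only α the SAP assigns to the primary outcome is one-sided 0.025, and the interval follows directly after the Fisher test of that outcome. With that α the written z is 1.96, the limits are those of an ordinary 95% interval, and only the label is wrong. The futility rule in SAP 9 also turns a one-sided p into z by the inverse Normal, which is the same mapping. The tipping-point threshold of 0.05, read as two-sided, is simply the counterpart of one-sided 0.025 and weak evidence for entering 0.05 in the interval.

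Much of this stands. The 0.025 reading is the better supported one, and the 90% interval is a conditional result that arises only if 0.05 is entered. Part of the disagreement with Fisher also has nothing to do with this defect: 4.3 of the 9.9 percentage points remain at z = 1.96, so the defect adds 9.9 − 4.3 = 5.6 points at 50% versus 25% and 3.4 − 0.8 = 2.6 points at 50% versus 50%.

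It does not clear the text. On the favourable reading the SAP still calls a 95% interval 97.5%, and a programmer who wants a 95% interval from a formula labelled 100(1−α)% will naturally enter 0.05. A divisor of 2 may have been lost when the PDF was read, but the printed percentile and the subscript on z agree with each other, and the missing numeric level would remain. The independent programming in SAP 11.2 is a limited safeguard, because both programmers work from the same specification.

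**Conclusion.** The concern holds. Label and formula disagree for every α between 0 and 1, and the SAP gives no number for the level. That the intervals are two-sided is inferred from the paired limits sharing one z; the SAP does not use the term for them. The remaining method 10 formulas are correct.

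If α is taken as 0.05, a nominal 90% interval would be reported as 95%. If α is taken as 0.025, the limits are right and only the label is wrong. The coverage, width and disagreement figures rest on 66 complete subjects per arm and the SAP's planning rates, with 50% in both arms for the null case. This is an error in how the primary estimate's precision is specified, and it should be corrected. It leaves the design and the primary test as they are.

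**What to change.** In SAP 7.1.1, define z as the 100(1−α/2)th percentile of the standard Normal, use one symbol for it throughout, and state that two-sided 95% intervals are reported (α = 0.05, z = 1.96), corresponding to the one-sided 0.025 test. Both parts are needed: correcting the percentile without writing the level leaves the z = 2.241 outcome possible.

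Add a sentence that Fisher's test is conservative and is not the inversion of method 10, so the two can still differ. At 33/66 versus 21/66, for example, Fisher p is 0.0255 and the 95% interval is 0.014 to 0.336.

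The cost is one or two lines, best made before the table specifications are written, which SAP 11.1 places after the SAP is finalised. The reported interval is wider than with z = 1.645 (mean width 0.310 against 0.262), and unchanged if z = 1.96 was already intended.

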## **3.0 ELIGIBILITY CRITERIA**

### **3.1a Screening Inclusion criteria**

1. Police officers who are scheduled for firearm training and/or certification on the range.
2. At least 18 years of age.
3. Air conduction thresholds are to be no worse than 25 dB HL from 0.5 kHz to 3 kHz, no worse than 30 dB HL at 4 kHz, and no worse than 45 dB HL at 6 and 8 kHz prior to shooting range exposure.

4. Observed air-bone gap < 10 dB HL at .5, 1, 2 and 4 kHz, with normal tympanometry.
5. Ability to understand and willingness to sign an IRB approved written informed consent document.

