3.1 Primary estimand

The primary estimand for the study is: In police officers who are training for firearm certification as part of their standard occupational requirements and suffer temporary threshold shift (TTS) following shooting range noise exposure, what is the difference in the proportion of officers experiencing PTS (defined as all officers who in audiogram are identified as having a permanent threshold shift (PTS) of ≥ 10 dB HL increase at any frequency from 2-6 kHz in at least one ear (30 days (+/- 3 days) post shooting - Baseline) to total number of subjects in each study arm/group) between ZNS treatment compared to Placebo, 30±3 days after randomization.

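### The supportive adjusted analysis gives a conditional odds ratio with baseline hearing cut in two, so its precision never reaches the risk difference that defines the estimand

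*SAP*

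**What the plan says.** The primary estimand (SAP 3.1) asks "what is the difference in the proportion of officers experiencing PTS" between the ZNS and placebo arms. SAP 3.2 states the hypothesis on the same scale, as an absolute reduction of 25 points.

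For the primary test, SAP 7.1.1 says that Fisher's "exact test will be used to compare the proportion of officers with PTS positive in ZNS group" with that in the placebo group. The same section gives an estimate and interval: "The proportion difference between groups is" D = p1 - p2, with limits by Newcombe's method 10. Neither the test nor the interval uses covariates.

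The adjusted analysis follows: "To provide an estimate of treatment effect a supportive logistic regression analysis will be done with covariates". The covariates are age, "pre-existing hearing loss dichotomized to normal to minimal hearing loss and slight to mild loss", noise history as high or low risk, and an average post-shooting quantity that the sentence does not name. In the ANCOVA of SAP 7.1.2 the matching term is the average post-shooting TTS. Sensitivity 2 shows the effect measure taken from the model: its OR "is the Odds ratio estimate for ZNS as compared to Placebo from the primary logistic regression analysis".

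Protocol 12.2.1 has the same logistic model but no risk-difference interval.

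**The concern.** A logistic regression coefficient compares officers who share the same covariate values. Averaged over officers, it does not give the difference in proportions. It does not give the marginal odds ratio either, because the odds ratio is non-collapsible: as the covariates become more predictive, the conditional odds ratio moves away from the marginal one even when the risk difference stays fixed.

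Two things follow. The adjusted and unadjusted results cannot be set side by side as two estimates of one quantity. And whatever precision baseline hearing and TTS size offer is spent on the odds-ratio scale and never reaches the risk difference.

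Cutting baseline hearing into two classes discards further information. Thresholds are measured in dB HL for each ear (Protocol 5.1), so a continuous value is available. Neither document gives the cut-off, the frequencies or the ear rule for the two classes, so the covariate cannot be programmed without a later choice.

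**Working it through.** **Inputs.** From SAP 2.7: 66 per group, PTS risks 50% and 25%, one-sided alpha 0.025, stated power 80.5%. The documents give no value for how strongly the covariates predict PTS. I assume one standard normal covariate x with strength b = 0.5, 1.0 or 1.5 log-odds per SD.

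**1. The plan's power.** The arcsine approximation to Fisher's test with continuity correction is Φ{√(2n)·[asin√(p1 - 1/2n) - asin√(p2 + 1/2n)] - 1.96}. With n = 66 this is Φ{11.489 × 0.2455 - 1.96} = Φ(0.861) = 80.5%. Full enumeration of the exact test gives 81.3%. The plan's figure reproduces, and it rests on the unadjusted test.

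**2. The unadjusted estimate.** With 33/66 against 17/66 events, D = 0.242 and the SAP's Newcombe formula (z = 1.96) gives 0.077 to 0.390. This estimates the SAP 3.1 quantity directly. The planning standard error is √[(0.50×0.50 + 0.25×0.75)/66] = 0.0814.

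**3. The conditional odds ratio.** Take logit(p) = a + b·x + t·group. Solve for a and t so that the risks averaged over x are 0.50 and 0.25. The marginal odds ratio is (0.25/0.75)/(0.50/0.50) = 0.333. By symmetry a = 0, and t = -1.158, -1.315 and -1.531, so exp(t) = 0.314, 0.268 and 0.216. The risk difference is 0.25 throughout.

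**4. Standard error of a standardised risk difference.** Let p0(x), p1(x) be the true risks and m0(x), m1(x) the risks the model can represent: equal to p0 and p1 for continuous x, and averages within each half for a median split. The large-sample variance with 132 officers is

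{2·E[p0(1-p0) + (p0-m0)²] + 2·E[p1(1-p1) + (p1-m1)²] + E[(m0-m1-0.25)²]} / 132.

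| b | conditional OR | SE unadjusted | SE, median split | SE, continuous | continuous v unadjusted | continuous v split |
|---|---|---|---|---|---|---|
| 0.5 | 0.31 | 0.0814 | 0.0801 | 0.0794 | 2.5% smaller | 0.9% smaller |
| 1.0 | 0.27 | 0.0814 | 0.0770 | 0.0747 | 8.2% smaller | 2.9% smaller |
| 1.5 | 0.22 | 0.0814 | 0.0734 | 0.0697 | 14.4% smaller | 5.1% smaller |

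**5. Check by simulation.** In 4,000 simulated trials per strength with 66 per arm, the standardised difference averaged 0.25 in every case. Standard errors with continuous x were 0.0791, 0.0750 and 0.0696, against 0.0806, 0.0809 and 0.0816 unadjusted: reductions of 1.9%, 7.3% and 14.6%.

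**6. Where the gain comes from.** Standardising with the split covariate already lowers the standard error by 1.6%, 5.5% and 9.9%, about two-thirds of the full gain. The change of scale matters more than undoing the dichotomy.

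**The case against.** The strongest reply is that the estimand already has an estimator. D with its Newcombe interval is marginal and on the right scale, and the SAP calls the logistic model supportive. That stands. A reader might infer that the estimand goes unestimated, or that the primary test or sample size is at fault. SAP 7.1.1 and step 1 show otherwise.

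Other strong readings also fail:

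- **A nearly empty hearing class.** The screening criterion begins "Air conduction thresholds are to be no worse than 25 dB HL from 0.5 kHz to 3 kHz", which suggests little spread. But it goes on to allow 30 dB at 4 kHz and 45 dB at 6 and 8 kHz, and 6 kHz lies in the PTS band. With no cut-off stated, class sizes cannot be inferred.
- **Secondary analyses that ignore continuous baseline.** The ANCOVA in SAP 7.1.2 already controls for each outcome's baseline value.
- **TTS size left out.** A post-shooting term is already in the logistic model, though incompletely named.
- **Precision counted as extra officers.** Fisher's test uses no covariates, so adjustment adds nothing to primary power.
- **A much more extreme odds ratio.** A strength of 2 log-odds per SD would give 0.17, but that means an odds ratio of 7.4 per SD, and nothing in the documents supports it.

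It is also speculation that a reader would take the odds ratio for a larger effect, since D is reported beside it.

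The Sensitivity 2 code has "model PTS = group AGE PTA LSurg" with PTA outside the CLASS statement, so hearing may be continuous there. That code is a template with unfinished terms and yields no risk difference. It also disagrees with the dichotomised covariate in the text.

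What remains is that no adjusted estimate of the estimand is planned, and that one baseline covariate is coarsened without a stated cut-off.

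**Conclusion.** The point holds as a modest, low-cost improvement to a supportive analysis. It is not an error in the primary inference. The adjusted result is on a different scale from SAP 3.1, and with a fixed 25-point difference it would read 0.31 to 0.22 depending only on assumed covariate strength.

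Carrying the adjustment to the risk difference would cut its standard error by about 2% to 14%. Continuous entry accounts for about 1% to 5% relative to a median split.

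These sizes assume b between 0.5 and 1.5, a single normal covariate and a correctly specified model. If baseline hearing carries only part of the prognostic strength, the loss from the split is smaller; an uneven split would lose more. If the covariates are weak, which restricted eligibility makes plausible, the gain is near the lower end.

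**What to change.** Keep the Fisher test and the Newcombe interval as they are. In SAP 7.1.1 and Protocol 12.2.1:

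- Specify the supportive logistic model with treatment, noise stratum, age, mean 2-6 kHz baseline threshold and mean 2-6 kHz Visit 3 shift, the last two continuous. State the ear rule for both means. The Visit 3 audiogram precedes randomisation and dosing, so the shift is a legitimate covariate.
- From that model, report the standardised (g-computation) risk difference with a 95% interval as the adjusted estimate of the SAP 3.1 estimand, and the odds ratio second.
- Name the variance method, delta or bootstrap, and combine estimates over the imputed datasets by Rubin's rules.
- Complete the unnamed post-shooting covariate. Reconcile the label supportive in the model description with primary in Sensitivity 2, and make the template code match the text.

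The cost is SAP wording and some extra programming. The small downside is an assumption of linear covariate effects with about 50 expected events (33 + 16.5). The change should be made before unblinding so that covariate form and scale are not chosen with results in view.

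### The tipping-point shift has no consistent sign or MAR anchor, and the placebo-based MNAR analysis is printed with the MAR code

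*SAP*

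**What the plan says.** SAP 7.1.1 lists two sensitivity analyses for missing primary-endpoint data. Protocol 12.2.1 carries the same text.

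**Sensitivity 1** is labelled MNAR. Missing values are to be imputed "using the distribution implied by the non-missing officer data within the placebo group". The PROC MI statements printed beneath are those that SAP 5.2 gives for imputation under MAR within each treatment group. The pooling step lists the intercept, age, PTA and one further covariate, followed by an ellipsis. The SAP 5.2 block pools `group`.

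**Sensitivity 2** is labelled "Logistic regression tipping point analysis under the assumption of data missing at random". A penalty of k × log(OR), with OR for ZNS relative to placebo, "will be added to imputed values in ZNS arm". The multiplier k "ranges from 1 (equivalent to MI approach based on MAR) to 0 (or higher"), and the printed list runs from 1 down to 0 and then on to 1.05 and 1.10. The search continues "until the conclusion of the primary analysis is overturned". The Step 2 comment says to "subtract DELTA derived above from their imputed data", and the code line is "mnar adjust(PTS / shift=DELTA adjustobs=(group='1" (closing characters omitted). Step 3 is headed "Apply the primary MMRM to the 10 complete datasets in Step 2".

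**The concern.** A tipping-point analysis asks how much worse the unobserved ZNS officers must be before the conclusion fails. For that, the shift must raise their imputed PTS risk, start from MAR and grow. The text fixes neither the direction nor the starting point, and three readings are open:

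- **(a) Added, as in the prose.** MAR is at k = 0, and every k > 0 lowers imputed PTS on ZNS.
- **(b) Placebo-anchored.** This makes k = 1 the MAR case and k = 0 the placebo level. ZNS is penalised only up to placebo level, and 1.05 and 1.10 favour ZNS.
- **(c) Subtracted, as in the comment.** This is a genuine penalty, but MAR is at k = 0.

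Other faults in the same text:

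- A delta shift is an MNAR method, and its code uses an MNAR statement, yet the label says missing at random.
- Step 1 already imputes PTS. If its output goes into Step 2, no missing PTS is left to shift.
- A binary endpoint tested with Fisher's exact test has no primary MMRM.
- If the printed Sensitivity 1 code is used, the MNAR analysis is the MAR analysis, and the treatment effect is not among the printed pooled terms.

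These are the plan's only two checks on missing primary data. As written, one may be unable to fail and the other may repeat MAR.

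**Working it through.** **Inputs from the plan.** 66 per arm, PTS 50% on placebo and 25% on ZNS (SAP 2.7); Fisher's exact test (SAP 7.1.1) at one-sided 0.025 (SAP 3.2); fewer than 5% missing (SAP 5.2), taken as 3 of 66 per arm (4.5%).

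**The plan's own figure.** Exact enumeration of the one-sided Fisher test at 66 per arm gives 81.3% power, against the stated 80.5%. The inputs are therefore read correctly.

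**Imputed PTS for a missing ZNS officer.** log(OR) = ln[(0.25/0.75)/(0.50/0.50)] = ln(1/3) = −1.0986.

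- (a) Added: expit(logit 0.25 + k·log OR)
- (b) Placebo-anchored: expit(logit 0.50 + k·log OR)
- (c) Subtracted: expit(logit 0.25 − k·log OR)

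| k | (a) added | (b) placebo-anchored | (c) subtracted |
|---|---|---|---|
| 0 | 25% | 50% | 25% |
| 1 | 10% | 25% | 50% |
| 1.05 | 9.5% | 24% | 51% |
| 2 | 3.6% | 10% | 75% |

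MAR is 25%. Shifting the MAR-imputed value by the stated formula does not give MAR at k = 1 with either sign. Only reading (b) does, and it needs a placebo base that the text does not state.

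**A borderline table (assumed).** ZNS 20/63 against placebo 32/63, 3 missing per arm, log OR −0.797. Fisher one-sided p = 0.023. Method: Rubin's rules for the risk difference in the many-imputation limit, no covariates, arm rates drawn from beta(r + 0.5, n − r + 0.5), normal reference. The pooled one-sided p under MAR is 0.0134.

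| k | (a) added | (c) subtracted |
|---|---|---|
| 1 | 0.0106 | 0.0177 |
| 2 | 0.0091 | 0.0225 |
| 3 | 0.0084 | 0.0266 |
| 4 | 0.0080 | 0.0292 |

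Reading (b) peaks at 0.0177, at k = 0. Reading (c) crosses 0.025 at k = 2.57, where imputed PTS is 78%. On the log-OR scale MAR gives 0.016 and (c) tips at about k = 2. With 16/63 against 32/63, no reading tips; the largest p is 0.0042.

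**All possible tables at 25% vs 50%.** The figures are shares of all trials that are Fisher-significant and then have pooled p ≥ 0.025 (risk difference). Fisher is significant in 79.4% of trials with 63 observed per arm.

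| Missing per arm | Reading | k = 1 | k = 2 | k = 3 | k = 4 |
|---|---|---|---|---|---|
| 3 | (c) subtracted | 0% | 0.15% | 3.9% | 5.9% |
| 6 (9%) | (c) subtracted | 0% | 7.1% | 14% | 17% |

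Readings (a) and (b) lose 0% at every k tried from 0 to 4, with 3 or 6 missing. Starting from a MAR-pooled significant result instead (84.5% of trials, 3 missing per arm), (a) loses 0%, (b) at most 3.0%, and (c) 3.0%, 5.2% and 10.9% at k = 1, 2 and 4.

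**The case against.** **A consistent anchor can be found.** If the shift is applied to the placebo log-odds, then the formula, the word added, k = 1 as MAR and the path from 1 to 0 all agree, and only a comment and the tail of the k list conflict. This is the best rescue, but it does not hold. The text says that data are imputed in each of the study groups, which is not a placebo base. The values above 1 still favour ZNS, and the stress stops at placebo level, so the search may end without overturning anything.

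**The event level is not stated.** On the log-odds of being PTS-negative, adding a negative log(OR) would penalise ZNS. That is correct for Step 2, and it is a further ambiguity. Step 3 models PTS with the descending option, which points to the PTS-positive scale used here.

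**The code is only a template.** It is offered as a form with ellipses, and `group` might sit behind one of them. No ellipsis supplies the missing MNAR statement in Sensitivity 1 or reconciles added with subtract, and the faults of sign, anchor, grid and label are in the prose too.

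**It rarely matters.** This stands. Over the printed values of k (0 to 1.10) with 3 missing per arm, no reading overturns a Fisher-significant result. On the log-OR scale, which matches Step 3, the subtracted losses are somewhat larger than on the risk difference (0.9% at k = 2, 5.9% at k = 3) but still small.

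**Conclusion.** The concern holds: the text is wrong as written, not merely short of detail. Followed literally, the tipping-point penalty helps ZNS and cannot tip a result that is significant under MAR. Subtracted, it can. The printed Sensitivity 1 code does not do what its description says.

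The practical size is small at the missingness the plan expects. At most 5.9% of trials at the design rates change conclusion for k up to 4 (3 missing per arm, risk-difference scale), and only borderline results are affected. With 6 missing per arm, above the plan's expectation, this rises to 17%. The observed tables, numbers missing and covariate-free imputation are assumptions. The primary test, its alpha and the sample size are untouched. Dataset and output specifications and double programming (SAP 11) might catch the conflict, but the choice of assumption should be fixed before unblinding. The change should be made, but it is not critical to the trial.

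**What to change.** In SAP 7.1.1 and Protocol 12.2.1:

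1. Define delta = −k × log(OR) on the log-odds of being PTS-positive for missing ZNS officers. Take k = 0 as MAR and k = 1 as roughly placebo level, with k rising beyond 1 until one-sided p ≥ 0.025. State which model supplies log(OR).
2. Make the Step 2 comment and code agree. Name the event level and the ZNS group code, and apply the MNAR adjustment in the step that imputes PTS.
3. Label Sensitivity 2 as MNAR and replace the MMRM reference with the logistic model (binomial, logit link).
4. Give Sensitivity 1 code that imputes from placebo only (MNAR MODEL with MODELOBS restricted to placebo). Pool the treatment effect by including `group` in MODELEFFECTS, on one named scale: log odds ratio, or risk difference with its standard error.

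The cost is text and sample-code edits in the two documents. Data collection, sample size and the primary test do not change.
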